Study Protocol and Statistical Analysis Plan

Clinical Study of Released Unitron RIC and
BTE Hearing Aid Models – ID# 515

January 4, 2022.

NCT05197803

Clinical Study of Released Unitron RIC and BTE Hearing Aid Models – ID# 515

1 Objectives and hypotheses of the clinical investigation

1.1 Purpose of the clinical investigation claims for clinical performance, effectiveness or safety of the investigational device that are to be verified

This clinical study intends to show that compared to the unaided condition, the released Unitron RIC and BTE hearing aid models provide amplification that will improve speech intelligibility when programmed for individual hearing losses. The study (and the resulting clinical data) will support the clinical benefit claim: “improved speech understanding” necessary to update the CER which is necessary for the CE submission. The claim will not be use externally or in any marketing material.

1.2 Primary and Secondary Objectives

The primary objective of this study is to confirm the improvement in the speech understanding with the released Unitron RIC and BTE hearing aid models in 20-25 participants with mild to severe hearing loss in a sound room/lab setting; testing will be performed with a standardized speech discrimination test – HINT in noise and the data will be collected during one-time visit.

2 Design of the clinical investigation

2.1 General

2.1.1 Design Type

This is a confirmatory study using a single group, unblinded in a single site. The data will be collected during one-time visit and results for each form factor will not be compared against each other but only against the unaided condition.

2.2 Procedures

2.2.1 Investigation-related Procedure

Participants will be selected from the existing database and based on their hearing loss; inclusion/exclusion criteria will be discussed. If necessary, an updated hearing test will be conducted prior to the start of data collection. Participants will be contacted via email and/or call to set up a time for the one-time visit. During the visit, participants will sign the consent form, they will be fit with the released Unitron RIC and BTE hearing aid models, and perform the HINT test in the sound room for the three study conditions: unaided, aided with RIC, and aided with BTE.

3 Statistical design and analysis

3.1 Determination of Sample Size

Although we have no prior data showing an estimated mean difference between unaided and aided conditions, we looked at the literature to estimate aided vs unaided benefit.

Valente & Mispagel (2008) investigated unaided and aided (Omni and Directional) HINT performance in adults with a sloping normal to moderately-severe SNHL. Results had shown that aided-directional HINT performance was significantly better than both unaided or aided-omni

conditions. The mean difference (1.7 dB) and SD (2.4) between unaided and aided-directional performance were used for the power analysis and ultimately calculating sample size.

Power Analysis was done using the G*Power Software (Faul et al., 2007). Power analysis was done for a one-tailed dependent t-test between two means. The table below list the input parameters used to calculate sample size.

Input parameters	Output parameters

• Mean of differences: 1.7• SD of differences: 2.4• Effect size dz: 0.708• Alpha=0.05• Power=0.95	
• Non centrality parameter: 3.40• Critical t: 1.72• Actual power: 0.95• Df: 22• Total sample size: 23

Based on the above calculations, it was determined that a minimum of 23 participants will be required based on a power analysis using arms-length data.

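### Does the 95% power fail to apply because the 1.7 dB effect comes from a directional-microphone condition that the plan does not tie to its own testing?

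*Combined protocol and SAP*

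**What the plan says.** Section 3.1 states that the sponsor had no data of its own on aided benefit and turned to the literature. The source study measured HINT performance unaided and with two aided settings, omnidirectional and directional. Section 3.1 summarises it thus: "Results had shown that aided-directional HINT performance was significantly better than both unaided or aided-omni". It then says which contrast was used: "The mean difference (1.7 dB) and SD (2.4) between unaided and aided-directional performance were used for the power analysis". It calls the input arms-length data.

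The trial's own procedure, in section 2.2.1, is brief. Of the participants it says "they will be fit with the released Unitron RIC and BTE hearing aid models", after which they take the HINT in three conditions: unaided, with RIC and with BTE. Section 1.1 adds that the devices are programmed to each person's loss. Section 1.2 specifies HINT in noise in a sound room and a target of "20-25 participants with mild to severe hearing loss". No section gives the microphone mode or the placement of speech and noise. The two modes are named only in section 3.1, and only to describe the source study.

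**The concern.** By the plan's own account, aided benefit depends on microphone mode, and the planning effect comes from the better of the two modes. If the Unitron devices were tested in omnidirectional mode, or in a mode that varied between participants, the mean benefit could be below 1.7 dB or the spread above 2.4. Power would then be under 95%, and a non-significant result might reflect the microphone setting and not a lack of benefit from amplification. The study is described as confirmatory and is meant to support a benefit claim in a regulatory file, so an overstated power figure would matter.

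The populations are also described differently. The source sample had sloping losses from normal to moderately severe; this trial enrols mild to severe. That seems to widen the gap between the borrowed effect and the trial.

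**Working it through.** **Inputs, all from section 3.1.** Mean difference 1.7 dB; SD of differences 2.4; alpha 0.05; target power 0.95. The test is given as "Power analysis was done for a one-tailed dependent t-test between two means".

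**Step 1: reproduce the plan's figure.**
- Effect size: dz = 1.7 / 2.4 = 0.708, matching "Effect size dz: 0.708".
- Noncentrality: dz × √n = 0.7083 × √23 = 3.397 (plan: 3.40).
- Critical value: t(0.95; 22 df) = 1.717 (plan: 1.72).
- Power = P(T > 1.717), where T is noncentral t with 22 df and noncentrality 3.397. This equals 0.950.
- The smallest n reaching 0.95 is 23, matching "Total sample size: 23".

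The arithmetic is correct for its stated inputs. Because 23 is the smallest such n, the 95% target itself has no reserve.

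**Step 2: how sensitive is the power to the effect?** The documents give no unaided versus omnidirectional difference, so the smaller effects below are assumptions. The formula is as in step 1, with SD 2.4 and one-tailed 0.05.

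| Assumed true difference | Power at n = 23 | n for 95% power |
|---|---|---|
| 1.7 dB (plan) | 0.950 | 23 |
| 1.5 dB | 0.896 | 30 |
| 1.3 dB | 0.808 | not calculated |
| 1.2 dB | 0.751 | 45 |
| 1.0 dB | 0.615 | 64 |
| 0.85 dB | 0.500 | 88 |

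Solving for the difference at fixed power with n = 23 gives 90% at 1.51 dB and 80% at 1.28 dB. Since 1.28 / 1.7 = 0.76, the true effect can be about 24% below the planning value before power falls under 80%.

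**Step 3: sensitivity to the spread.** At 1.7 dB and n = 23, power is 0.989 with an assumed SD of 2.0 and 0.880 with an assumed SD of 2.8.

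**Step 4: do the sections conflict?** Section 3.1 assumes a directional contrast. Sections 1.1, 1.2 and 2.2.1 say nothing about mode: they do not specify omnidirectional, automatic or mixed. Silence is compatible with directional testing, in which case 1.7 dB may be the matching contrast. No two statements contradict each other.

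**Step 5: the population difference.** The trial's range begins and ends at greater loss than the source sample's. The documents do not say whether that raises or lowers aided benefit, so it cannot be counted as a loss of power.

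**The case for a change.** The best case for a change is this. The plan rests its whole sample-size argument on one borrowed contrast, admits that it has no data of its own, reports that the contrast depends on mode, picks the larger effect without giving a reason, and then does not fix the mode. Two sentences naming the mode and the HINT layout would close the gap, and a line showing power at smaller effects would make the 95% visibly conditional. Going to the upper limit of 25 participants would not rescue a 1.0 dB effect, where power is only 0.648.

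Much of this stands as description. The set-up is unstated, and a reader would be better served by knowing it. A non-significant result would also have to be read with the mode in mind.

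What does not stand is the step from there to a fault in the plan. The size of any shortfall is unknown. A different layout or newer devices could give a larger effect as easily as a smaller one. The remedies are also weak. Recording the mode completes the description without altering the analysis, although imposing a single mode and layout would constrain procedures if these now vary. A table at assumed effects changes no decision. Rebasing the sample size needs an effect that the documents do not supply, and it is not free: if that effect were smaller, keeping 95% power would take 30 participants at 1.5 dB or 64 at 1.0 dB, both above the planned 20 to 25.

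**Conclusion.** No change follows. This is a gap in description of the kind that the study team fills when it sets up the test. Each participant is compared with himself or herself unaided, so the planning effect has no bearing on the validity of the t-test or its error rate. It bears only on the chance of success. That chance is stated correctly for an assumption whose source and condition are named openly.

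The 95% is best read as conditional on a directional set-up comparable to the source study's. If the true benefit is lower, power with 23 participants would be about 0.90 at 1.5 dB, 0.81 at 1.3 dB and 0.62 at 1.0 dB, assuming SD 2.4 and a one-tailed 0.05 test. The documents do not show that any of these lower values applies. Reporting the mode and noise layout with the results would be helpful, but is optional.

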3.2 Statistical criteria of termination of trial

There is no statistical criteria that would cause termination of the trial.

3.3 Planned Analysis

The data analysis will be done upon completion of data collection. A one-tailed t-test will be done as part of the analysis.

3.3.1 Datasets to be analyzed, analysis population

- Analysis population: 20-25 participants
- Data sets:
 - Unaided vs. aided with RIC.
 - Unaided vs. aided with BTE.

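### Section 3.1 requires at least 23 participants for 95% power, but 1.2 and 3.3.1 allow 20-25; at 20-22 the power per comparison is 92-94%.

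*Combined protocol and SAP*

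**What the plan says.** Section 3.1 (Determination of Sample Size) describes the method: "Power analysis was done for a one-tailed dependent t-test between two means". Its inputs are "Mean of differences: 1.7" and "SD of differences: 2.4" (in dB, from a published hearing-aid study), with alpha 0.05 and power 0.95. The output is "Total sample size: 23", and the section concludes that "it was determined that a minimum of 23 participants will be required based on a power analysis using arms-length data".

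Two other sections give a range that starts lower. The primary objective in 1.2 is to be confirmed "in 20-25 participants with mild to severe hearing loss in a sound room/lab setting". Section 3.3.1 then states "Analysis population: 20-25 participants" and lists two data sets, unaided against each aided condition.

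Section 2.1.1 (Design Type) confirms that "results for each form factor will not be compared against each other but only against the unaided condition", so the power calculation in 3.1 applies to each aided condition separately.

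**The concern.** A required minimum of 23 and a permitted sample of 20 cannot both stand. A study that finished with 20, 21 or 22 participants would comply with 1.2 and 3.3.1 and breach 3.1, so the plan would give opposite answers on whether the sample was adequate.

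Section 2.1.1 calls the study confirmatory, and section 1.1 says its data will support a clinical benefit claim needed for the CE submission. The number of participants that counts as enough should therefore be fixed before data collection. Section 3.2 sets no statistical criterion for termination, so nothing else in the plan settles the number.

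**Working it through.** **Inputs, all from section 3.1.** Mean of the paired differences 1.7 dB; SD of the differences 2.4 dB; one-tailed alpha 0.05; target power 0.95.

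**Formulas.**
- Effect size: dz = mean / SD = 1.7 / 2.4 = 0.7083
- Noncentrality: ncp = dz × √n
- Degrees of freedom: n − 1
- Critical value: the 95th percentile of the central t distribution on n − 1 degrees of freedom
- Power: the probability that a noncentral t variable with n − 1 degrees of freedom and this ncp exceeds the critical value

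**Step 1: reproduce the plan's figure.** At n = 23, ncp = 0.7083 × √23 = 3.397, df = 22, critical t = 1.717 and power = 0.9500. The table in 3.1 gives 3.40, 22, 1.72 and 0.95. They agree, and 23 is the smallest n that reaches 95%.

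**Step 2: apply the same calculation to every size that 1.2 and 3.3.1 permit.**

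| n | ncp | Critical t | Power per comparison | Difference from 95% (points) |
|---|---|---|---|---|
| 20 | 3.168 | 1.729 | 0.9203 | −3.0 |
| 21 | 3.246 | 1.725 | 0.9317 | −1.8 |
| 22 | 3.322 | 1.721 | 0.9415 | −0.85 |
| 23 | 3.397 | 1.717 | 0.9500 | 0.0 |
| 24 | 3.470 | 1.714 | 0.9573 | +0.7 |
| 25 | 3.542 | 1.711 | 0.9636 | +1.4 |

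A simulation with normally distributed differences (400,000 trials per size) gave 0.9204, 0.9319, 0.9415, 0.9502, 0.9577 and 0.9631 for n = 20 to 25, which agrees.

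**Step 3: express the shortfall in dB.** The dz needed for 95% power is 0.764 at n = 20, 0.744 at n = 21 and 0.725 at n = 22. Multiplying by the SD of 2.4 gives true mean differences of 1.83, 1.79 and 1.74 dB, against the assumed 1.70 dB.

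**Step 4: look for a reading that reconciles the sections.**
- *20-25 is enrolment and 23 is the analysed number.* Section 3.3.1 applies 20-25 to the analysis population itself.
- *20 allows for dropout.* The plan does not mention dropout and collects all data in one visit. An allowance would in any case raise the recruitment target, not lower the analysed number.
- *A lower power is acceptable.* Section 3.1 names only 0.95.

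**The case against.** The strongest reply is that this is loose wording more than a contradiction. The range 20-25 contains 23, and a sample of 23 to 25 satisfies all three sections. Section 3.1 is where sample size is decided and it uses binding language, whereas 1.2 and 3.3.1 never say that 20 is sufficient. A reader could reasonably let 3.1 control and treat 20-22 as falling short. That is fair as a guess at intent. It does not remove the mismatch, because two sections still print a lower limit of 20 and one of them defines the analysis population by it.

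The second reply is that the effect is small beside the uncertainty in the inputs. Section 3.1 says the sponsor has no prior data of its own and takes the difference and SD from one publication. As an illustration with assumed values, an SD of 2.5 instead of 2.4 lowers power at n = 23 to 93.5%, and a mean of 1.6 dB instead of 1.7 lowers it to 92.7%. These shifts (1.5 and 2.3 points) are similar to the losses at 21 and 22 participants. This stands: the differences among 20 to 23 should not be read as a sharp threshold. It limits the weight of the point but does not make the sections agree.

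The third reply is that the power figures are per comparison. The plan has two comparisons, and power to succeed on both can be no higher than the figures above. This is correct, and the table should be read that way.

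**Conclusion.** The concern holds, as a minor inconsistency. The sample-size calculation is right, but the range in 1.2 and 3.3.1 was not aligned with it, and three of the six permitted sizes miss both the stated minimum and the stated power. The shortfall is 0.85 to 3.0 percentage points per comparison, and every permitted size keeps at least 92% power. The study is not seriously underpowered at any of them.

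These figures rest on the plan's own inputs: the assumed mean and SD, a one-tailed paired t-test at 0.05 without adjustment for the two comparisons, normally distributed differences, and the same effect for both aided conditions.

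**What to change.** Make the three sections agree in one of two ways.

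1. **Keep the minimum of 23.** Change 20-25 to 23-25 in section 1.2. In 3.3.1, state the analysis population as 23-25 participants with evaluable HINT scores for each aided-versus-unaided comparison. This stays within the existing maximum of 25 but may need up to three participants more than the present lower limit. Because the number evaluable is known only after testing, the text should also say what happens if it falls below 23.

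2. **Keep the range of 20-25.** Delete the statement of a 23-participant minimum in 3.1 and write instead: *On these inputs 23 participants give 95% power per comparison; the planned 20-25 participants give 92% (n=20) to 96% (n=25).* This needs no extra participants. Its price is a slightly less favourable stated power and the loss of the plan's only explicit minimum, so 20 would become the working lower limit.

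Both options are wording edits. The choice is the sponsor's and should be recorded before data collection.

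### Does leaving the final sample size open between 20 and 25 in an unblinded study undermine the 5% one-tailed error rate?

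*Combined protocol and SAP*

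**What the plan says.** Section 3.3.1 sets "Analysis population: 20-25 participants", and the same range stands in the primary objective (section 1.2). Section 3.1 calculates 23 and calls that the minimum. No section states how the final number is picked.

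On conduct, section 2.1.1 states: "This is a confirmatory study using a single group, unblinded in a single site". Each participant attends once and is tested unaided, with the RIC and with the BTE (section 2.2.1).

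On timing and stopping, section 3.3 states: "The data analysis will be done upon completion of data collection". Section 3.2 states: "There is no statistical criteria that would cause termination of the trial". The test is one-tailed: "A one-tailed t-test will be done as part of the analysis". Section 3.3.2 gives the significance analysis to an assigned statistician.

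**The concern.** A fixed-sample t-test holds its 5% level only if the sample size does not depend on the scores. Here any number from 20 to 25 satisfies sections 1.2 and 3.3.1, so the end of data collection is not a fixed event. Both paired differences for a participant exist as soon as that participant's visit is over, and nobody is blinded to condition. A team watching the differences build up could close enrolment at 20 if the result looked good, or carry on to 25 if it did not.

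That would be optional stopping against an unadjusted critical value. The study calls itself confirmatory, and its conclusion is a significance call for each device against unaided, so an inflated error would bear directly on the claim of improved speech understanding.

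**Working it through.** **Inputs.** From section 3.1: "Mean of differences: 1.7" dB, "SD of differences: 2.4" dB, one-tailed alpha 0.05, power 0.95. From sections 1.2 and 3.3.1: 20 to 25 participants. From section 3.1: a minimum of 23.

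**Step 1: the plan's own figure.** The section says: "Power analysis was done for a one-tailed dependent t-test between two means". The effect size is dz = 1.7/2.4 = 0.708. At n = 23 the noncentrality is 0.7083 × √23 = 3.397. The critical value is the 95th percentile of t on 22 df, 1.717. Power is 1 − F(1.717; 22 df, noncentrality 3.397) = 0.950, where F is the noncentral t distribution function. The stated 23 reproduces. The same formula gives 0.920 at 20 and 0.964 at 25.

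**Step 2: error if the plan is followed.** Let N be the final number and T_n the paired t statistic on n participants, tested against its own critical value. Then

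P(reject) = Σ P(N = n) × P(T_n > t(0.95, n−1) | N = n).

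If N does not depend on the scores, each conditional probability is 0.05, and the sum is 0.05 × Σ P(N = n) = 0.05. A variable N does not inflate the error by itself. The 5% holds at 20, at 25, or at any result-independent mixture.

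**Step 3: error if the results pick N.** For one comparison, no rule for choosing N within a set of permitted values can reject more often than P(at least one T_n in the set exceeds its critical value). This was simulated under zero true benefit with normal paired differences (2,000,000 null trials per row; the SD does not matter, because t is scale-free).

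| Numbers at which the team may stop | One-tailed error, one comparison |
|---|---|
| one fixed number | 5.0% |
| 20 or 25 | 6.9% |
| 20, 23 or 25 | 7.5% |
| every number from 20 to 25 | 8.2% |
| 23, 24 or 25 | 6.5% |

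The simulation standard error of the largest figure is √(0.082 × 0.918 / 2,000,000) = 0.0002, or 0.02 percentage points.

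The largest possible excess is therefore 8.2 − 5.0 = 3.2 percentage points over the full range, and 6.5 − 5.0 = 1.5 points if the minimum of 23 is respected.

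**Step 4: what the upper bound needs.** To reach 8.2% the team would have to test after each participant from the 20th on, stop at the first significant result, accept numbers below the stated minimum, and aim at one device. One sample serves both devices. If stopping instead required both tests to be significant, the per-comparison error would be about 6%, assuming a correlation of 0.5 to 0.8 between the two differences (the documents give none).

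**Step 5: the text against that scenario.** Testing before collection ends departs from section 3.3. Closing enrolment because a test is significant is a statistical criterion for ending, which section 3.2 says does not exist. Stopping below 23 departs from section 3.1.

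**The case for a change.** The best case for a change is that sections 3.2 and 3.3 do not quite close the gap. Completion of data collection is undefined, and ending at 20 need not count as termination in a plan that permits 20. No sentence bars anyone from looking at the scores as they accumulate. Nor is a formal interim test needed: an impression of the running differences could sway the decision to book more visits. Keeping the minimum of 23 leaves up to 6.5%, and naming one number would cost almost nothing.

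Part of this stands. The plan does not name the final number, and the bounds in the table are correct for the conduct they describe. The rest does not carry. Being unblinded means that tester and participant know the listening condition. It does not mean that whoever closes recruitment follows a cumulative t statistic, and the documents do not say who makes that decision. An informal impression is a poorer guide than an exact test after each participant, so its effect cannot exceed the bounds. The motive is also weak on the plan's own assumptions, since power is already 0.920 at 20 participants. What is left is the possibility of undeclared misconduct, which a small range around a planned size neither invites nor reveals.

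**Conclusion.** No change follows. With one analysis after collection and no statistical criterion for ending, the plan as written keeps the one-tailed error at 5.0% per comparison for any final number from 20 to 25. The figures of 6.5% (23 to 25) and 8.2% (20 to 25) are upper bounds for undisclosed stopping on the results, aimed at a single comparison. They measure a departure from the plan.

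The unstated enrolment endpoint is a gap that the team can fill sensibly, for instance by how many eligible people from the database attend, without any wrong result. This rests on the final number being settled without regard to the HINT differences, which is the plain reading of sections 3.2 and 3.3, and on normal paired differences for the simulated bounds.

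Two neighbouring matters are not decided here: the conflict between a range starting at 20 and a stated minimum of 23, which concerns power (0.920 at 20 against 0.950 at 23), and the testing of two devices, which concerns multiplicity.
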